6.1.11.3 Composite Score

Unless otherwise specified, any individual missing item in any scale won’t be imputed. When calculating a total score, subscale score, composite score, or any assessment with more than one item (e.g. Y-BOCS-BE total score and 2 subscale scores, EDE-Q global score and 4 subscale scores, EDE-QM global score and 3 subscale scores, SDS total score and 3 subscale scores, MADRS total score, HAM-A total score, CSSA total score, DESS total score), if one or more items are missing at a visit, then the associated score (ie, total score or subscale score) will be set to missing.

In the event of missing data at Week 12 for efficacy variables, the last post-baseline observation carried forward (LOCF) approach is used to impute missing values in the ITT LOCF efficacy analyses. Unscheduled visits are included in the imputation.

For analyses of the change from baseline for a given efficacy parameter, only subjects who have both baseline and at least one post-baseline measurement are included.

6.1.11.4 Incomplete/Missing Dates

6.1.11.4.1 Start/End Dates for Adverse Event

Treatment-emergent adverse events (TEAEs) are those events with an onset date on or after the start of double-blind study medication, through 7 days after study drug discontinuation (14 days for serious adverse events and deaths) for subjects who complete or discontinue this study but do not enter into the extension study), or through the last study day of the double-blind treatment period for subjects continuing into the extension study. A conservative approach will be used to handle the missing dates for AE onset date and end date to identify the treatment-emergent AE (ie, if the available incomplete date cannot determine treatment emergent status, the AE will be considered as a treatment-emergent AE). No imputation is done to calculate AE duration.

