15.4.2.1. Adverse Events

All AEs will be coded using Medical Dictionary for Regulatory Activities (MedDRA) version 18.0 or higher.

The terms used in the CRFs by Investigators to identify adverse events.

An adverse event (AE) is defined as having a start date on or after the date of first dose through 7 days after study drug discontinuation (14 days for serious adverse events and deaths) for subjects who complete or discontinue this study but do not enter into the extension study), or through the last study day of the double-blind treatment period for subjects continuing into the extension study.

A discontinuation-emergent adverse event (DEAE) is defined as an AE with a start date after the date of last dose of study drug through the last study visit in the withdrawal period for subjects who either complete the 12-week treatment period but do not enter into the extension study, or for subjects who are terminated early in the treatment period.

The summary of overall AEs (and SAEs) will be limited to AEs and DEAEs.

The overall incidence (ie, number and percent of subjects with one or more AE in each category) of AEs, serious AEs, deaths, AEs leading to discontinuation, study drug-related AEs, serious study drug-related AEs, study drug-related AEs leading to discontinuation, and serious AEs leading to discontinuation, serious study drug-related AEs, will be summarized by treatment group.

The AEs also will be summarized by system organ class (SOC) and preferred term (PT) by presenting the number and percentage of subjects with each AE category. The incidence of AEs (by PT, grouped by SOC, and presented by treatment group) also will be summarized by severity, by the relationship to study medication, by the action taken regarding the study medication, as well as by the outcome.

The overall incidence of DEAEs and serious DEAEs will be summarized by treatment group. The DEAEs also will be summarized by SOC and PT by presenting the number and percentage of subjects with each AE category.

The incidence of AEs of special interest, including but not limited to neuropsychiatric-related and cardiovascular-related AEs, will be summarized by treatment group.

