During the study and prior to database lock, the treatment assignments for all subjects are provided to the Bioanalytical Contract Research Organization (CRO) to facilitate plasma PK sample handling and analysis. No PK samples are analyzed for placebo subjects.

Protocol and IRT Amendment for Stratification Factor of Region

For this US study, there is no concern of ‘region’ difference for treatment effect. Sponsor’s initial intention of including stratification factor of region was to provide an optimization approach to ensure a balanced treatment assignment within each region. It should be noted that stratification by region was not implemented in study SEP360-221, which is also a US study with a similar study design.

The study team noticed on July 20, 2017 that the stratification by region was not implemented as planned, ie, the initiated sites in IRT were linked to incorrect regions (See [Section 6.1.5.1](#) for details). As of July 20, 2017, among 50 planned sites of this study, a total of 44 sites were screening subjects; and 137 subjects from 35 sites had already been randomized. Due to the ‘random’ nature of the incorrect assignment of region according to the root cause of this incident, the study team decided to remove stratification criteria related to ‘region’ to minimize the impact of this mistake. Stratification criteria were amended in study protocol V3.00 and randomization is to be balanced using only permuted blocks with baseline number of binge eating days per

321

week (3 – 4 binge eating days per week, > 4 binge eating days per week).

4. Changes in Planned Analyses

There is not any change made in this SAP from the analyses planned in the protocol.

5. Efficacy and Safety Variables

[Section 6.1.2](#) provides definitions of DB Baseline and Withdrawal Baseline. For the sake of simplicity, hereafter, Baseline and DB Baseline will be used in an interchangeable way.

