7.4.2 Adverse Events

All AEs are coded using Medical Dictionary for Regulatory Activities (MedDRA) version 18.0 or higher.

Treatment-Emergent Adverse Event (TEAE)

A treatment-emergent adverse event (TEAE) is defined as an AE with a start date on or after the date of first dose through 7 days after study drug discontinuation (14 days for serious adverse events and deaths) for subjects who complete or discontinue this study but do not enter into the extension study), or through the last study day of the double-blind treatment period for subjects

continuing into the extension study (ie, subjects in safety population). AEs with a start date prior to initiation of double-blind study medication which are reported to have an increase in intensity, or which are reported to have a attribution in relationship to study medication (ie, attribution to possible related, probably related, related) after the initiation of double-blind study medication are considered as TEAEs.

Discontinuation-emergent adverse event (DEAE) is defined as an AE with a start date after the last dose day of study medication through the last study visit in the withdrawal period.

Table summary of overall AEs (and SAEs) will be limited to TEAEs and DEAEs. All AE data will be displayed in data listings. For sake of simplicity, hereafter TEAE is referred as AE in this section.

The overall incidence (ie, number and percent of subjects with one or more AE in each category) of AEs, serious AEs, deaths, AEs leading to discontinuation, study drug-related AEs, serious study drug-related AEs, study drug-related AEs leading to discontinuation, and serious AEs leading to discontinuation, serious study drug-related AEs, will be summarized by treatment group.

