The AEs also will be summarized by system organ class (SOC) and preferred term (PT) by presenting the number and percentage of subjects with each AE category. The incidence of AEs (by preferred term, grouped by SOC, and presented by treatment group) will also be summarized by severity, by the relationship to study medication, by the action taken regarding the study medication, as well as by the outcome. If a subject has the same AE on multiple occasions, the highest severity (severe, moderate, mild) recorded for the event and the highest drug relationship (unrelated, unlikely to be related, possibly related, probably related, and definitely related) will be presented, respectively. The relationship to study medication will be presented by 2 categories: related (which includes possibly related, probably related, and related, as determined by investigators), and not related (which includes unrelated and unlikely to be related, as determined by investigators). Furthermore, for AE summary by SOC and PT or PT only, the following combined preferred terms will be summarized as well:

- Insomnia: Insomnia, Initial insomnia, Middle insomnia, Terminal insomnia.
- Hallucination: Hallucination; Hallucination, auditory; Hallucination, gustatory; Hallucination, olfactory; Hallucination, synaesthetic; Hallucination, tactile; Hallucination, visual; Hallucinations, mixed; Hypnagogic hallucination; Hypnopompic hallucination; Somatic hallucination.

A Kaplan-Meier plot of the time to the first onset of treatment emergent insomnia (combined term) will be presented by treatment group. Time to the first onset (in days) is defined as the earliest onset date of insomnia – start date of DB treatment period + 1. Subjects who do not experience any insomnia on or before the last dose date will be censored on the day of last dose.

321

Prevalence rate of insomnia (combined term) at a study day in the DB treatment period is defined as number of subjects experiencing insomnia on the day divided by number of subjects remaining on DB treatment period at that time point. It is notable that subjects may experience multiple insomnia episodes during the study. Prevalence rate over time will be presented graphically by treatment group.

AE maximum relationship

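### SAP 6.1.11.4.1 and 7.4.2 define a treatment-emergent event differently for pre-dose starts, and the insomnia time-to-event formula fails for those cases (minor)

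*SAP*

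**What the plan says.** Three places define which adverse events enter the on-treatment summaries.

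- **Protocol 15.4.2.1** sets the analysis rule by start date: "An adverse event (AE) is defined as having a start date on or after the date of first dose through 7 days". The window closes 7 days after stopping study drug (14 for serious events and deaths), or at the last double-blind day for subjects who enter the extension. The protocol says AE and never uses the term treatment-emergent, but it limits its summaries to these events and to discontinuation-emergent events (DEAEs).
- **SAP 6.1.11.4.1**, under incomplete and missing dates, uses the same window and the label TEAE: "Treatment-emergent adverse events (TEAEs) are those events with an onset date on or after the start of double-blind study medication". It then adds a conservative rule for incomplete dates.
- **SAP 7.4.2** opens with the same date rule, "A treatment-emergent adverse event (TEAE) is defined as an AE with a start date on or after the date of first dose", and then adds two routes for events that started before dosing. The first is "AEs with a start date prior to initiation of double-blind study medication which are reported to have an increase in intensity". The second covers those "which are reported to have a attribution in relationship to study medication". In both, the change must come after dosing starts. The overall AE tables are limited to TEAEs and DEAEs.

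SAP Section 4 states: "There is not any change made in this SAP from the analyses planned in the protocol".

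SAP 7.4.2 also plans a Kaplan-Meier plot of first treatment-emergent insomnia. "Time to the first onset (in days) is defined as the earliest onset date of insomnia", less the treatment start date, plus 1.

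**The concern.** Two sections of one SAP give different answers for an event with a pre-dose start, and neither refers to the other. A programmer working from 6.1.11.4.1 would leave out records that a programmer working from 7.4.2 would count. The wider definition also departs from the protocol's rule, yet Section 4 says nothing has changed.

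The insomnia plot adds a gap inside 7.4.2 itself. It claims to show treatment-emergent cases but dates them from onset, so a case admitted through either added route has no usable event time. Insomnia heads the list of common AEs reported from the earlier BED study (protocol 4.2). The SAP gives it a combined term, this plot and a prevalence curve, so its rule ought to be complete.

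**Working it through.** The documents state no figure to reproduce, so the check sets the definitions against the same records.

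**Classification.** The days are illustrative.

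| Record | Protocol 15.4.2.1 | SAP 6.1.11.4.1 | SAP 7.4.2 |
|---|---|---|---|
| A. Starts on Day 5 | counted | counted | counted |
| B. Starts before Day 1, worsens on Day 10, same record | not counted | not counted | counted |
| C. Starts before Day 1, unchanged, later judged possibly related | not counted | not counted | counted |
| D. Present before Day 1, worsening entered as a new record starting Day 10 | counted | counted | counted |
| E. Starts before Day 1, neither worsens nor is attributed | not counted | not counted | not counted |

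The definitions part only on B and C.

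**Where B and C can come from.**

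1. Relevant conditions present at entry are collected as medical history (protocol 11.1; SAP 7.1.8), not as event records.
2. Protocol 12.1.1 gives untoward occurrences between consent and first dose their own name, pre-treatment events. Protocol 12.3 requires them on the CRF, so such records can exist.
3. Protocol 12.1.1 also allows an exacerbation of a pre-existing condition to be an AE. If the site opens a new record with a post-dose start, the case is D and all three definitions agree.
4. What remains is an event first recorded between consent and first dose, kept under its pre-dose start date, that later worsens or is attributed to drug.

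**Scale.** The planned arm size is 160 (protocol 15.1). One subject counted under one definition but not the other moves an arm's incidence by 1/160 = 0.00625, or about 0.6 percentage points. The documents do not say how many such subjects to expect.

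**Insomnia event time.** Time = onset date − treatment start date + 1.

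- Onset on the first dosing day: 0 + 1 = 1.
- Onset the day before: −1 + 1 = 0.
- Onset 22 days before, the start of the planned screening window (Day −22): −22 + 1 = −21.

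A case that is treatment-emergent only through an added route therefore gets a time between 0 and −21 on the planned schedule, whenever the worsening occurred. The censoring rule does not take it in either, because that rule covers subjects with no insomnia up to the last dose.

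**The case against.** The best defence is that the operative text is clear enough. SAP 7.4.2 is the dedicated AE analysis section, and SAP 6.1.1.3 sends the reader there for when AE data count as on treatment. The sentence in 6.1.11.4.1 only introduces a missing-date rule. Protocol Section 15 leaves detail to the SAP. Most worsening of existing conditions will be entered as new AEs and counted under every definition. The AE summaries are descriptive, and the plot is one display.

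Most of this stands, and it is why the point is minor. It does not remove the inconsistency. Nothing says that 7.4.2 overrides 6.1.11.4.1, and the missing-date rule is attached to the narrower definition. Counting a class of events that the protocol's start-date rule leaves out goes beyond added detail. The time formula is incomplete even if 7.4.2 alone governs.

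A reader might go further and infer that the date-only rule would noticeably shrink the drug-placebo difference in insomnia or anxiety, because many subjects arrive with these conditions. The documents do not support that. Conditions at entry go to medical history, so their prevalence does not measure the gap. Permitting sleep aids during the study (protocol 10.3.3) does not show that insomnia is common at entry.

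**Conclusion.** The inconsistency is real and minor. For a record that starts before dosing and then worsens or is attributed to drug, SAP 7.4.2 gives a different flag from SAP 6.1.11.4.1 and protocol 15.4.2.1, and Section 4 does not declare the difference. The insomnia formula gives those same cases a zero or negative time.

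The number affected is probably small and cannot be estimated from the documents; the only firm scale is about 0.6 points of one arm's incidence per subject. That the number is small assumes that sites enter entry conditions as medical history and most exacerbations as new AEs.

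It would also be too strong to say that every AE table depends on this flag. DEAE tables have their own definition, and the full AE listing ignores treatment-emergent status. No efficacy conclusion is touched.

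**What to change.** 1. Keep a single TEAE definition in SAP 7.4.2. Replace the definition in 6.1.11.4.1 with a cross-reference and retain there only the rule for incomplete dates.
2. List the two added routes in SAP Section 4 as a change from protocol 15.4.2.1.
3. For the insomnia plot, take the date of worsening on or after Day 1 as the event date when the start was pre-dose. If that date is not collected, state that the plot is restricted to onsets on or after Day 1.

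The cost is SAP wording before database lock. No new data collection is needed, because the second option in item 3 covers the case where no worsening date exists.

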6.1.11.4.2 Start/End Dates for Prior/Concomitant Medication

Partial dates of non-study medication start/end date need to be imputed in order to classify the medications as prior or concomitant medications, or post-treatment medication (ie, medication initiated after the last dose of study medication). A conservative approach will be used to handle the incomplete date(s) for medication start/end date (ie, if the available incomplete date(s) cannot determine the concomitant relationship relative to the double-blind phase, the medication is considered as a concomitant medication).

6.1.11.4.3 Psychotherapy Dates /Psychiatric History Dates

Partial dates of initial symptoms of BED, initial diagnosis of BED, and psychotherapy will be imputed as follows: (1) If year and month are known, and if the year or month is previous to Screening, use the 15th of the month; otherwise, if the month is the month of Screening, use the 1st of the month. (2) If only year is known, and it is previous to the year of Screening, use June 30th of that year; If only year is known and it is same as the year of Screening, use Jan 1. This imputation rule will be applied to calculation of duration of initial symptoms of BED, initial diagnosis of BED, and psychotherapy.

6.1.11.4.4 Lab Data

Where applicable, the upper limit of quantification (ULOQ) will be imputed for chemistry, hematology, urinalysis, and urine microscopic values that are greater than the ULOQ. Similarly, if the value is below the lower limit of quantification (LLOQ), then the LLOQ will be imputed.

6.2. Methods of Analysis

6.2.1 General Methodology

All statistical inference analyses will be performed with 2-sided tests at a significance level of 0.05, and 2-sided 95% confidence intervals (CIs) will be calculated whenever appropriate. All

321

data will be summarized by treatment group and visit as appropriate. All subject data will be presented in data listings by subject.

Data for unscheduled assessments will be included when deriving baseline values and the worst case analysis during an assessed period. Unscheduled visits will also be included in treatment endpoint (Week 12 LOCF), which is the last available non-missing treatment endpoint carried forward to Week 12.

6.2.2 Statistical Hypotheses for Trial Objectives

6.2.2.1 Hypotheses for Primary Objective

In adults with moderate to severe BED, after 12 weeks of treatment,

- Dasotraline 6 mg/day reduces change from baseline in the number of binge days per week relative to placebo
- Dasotraline 4 mg/day reduces change from baseline in the number of binge days per week relative to placebo

6.2.2.2 Hypotheses for Key Secondary Objectives

In adults with moderate to severe BED, after 12 weeks of treatment, 6 mg/day dasotraline or both doses of dasotraline:

- Reduce change from baseline in BE-CGI-S score relative to placebo
- Provide a greater proportion of subjects with a 4-week cessation from binge eating at Week 12 relative to placebo
- Reduce change from baseline in Y-BOCS-BE total score relative to placebo

6.2.3 Interim Analysis

Not Applicable.

6.2.4 Data Monitoring

[figure not shown]
Data and Safety Monitoring Board (DSMB) meetings are planned to be held at regular intervals. Data to be presented to the DSMB are described in its charter.

6.2.5 Multiple Comparisons/Multiplicity

To control the overall type I error rate strongly at 5% for the primary and key secondary endpoints, for the hypotheses to be tested, a sequential testing strategy will be used. Following the fixed sequence closed testing procedure in [Figure 1](#), testing will only proceed conditional on the statistical significance of the test(s) of prior level(s) at a 2-sided 5% significance level.

321

Figure 1: Fixed Sequence of Hypothesis Testing for Primary and Key Secondary Efficacy Endpoints

Denote raw p -values associated with hypotheses H_1 to H_8 as p_1 to p_8 . Adjusted p -value of raw p -value of each testing hypothesis is calculated as below.

$$p_{1_adj} = p_1,$$

$$p_{i_adj} = \max(p_i, p_{i-1_adj}), \quad i = 2, \dots, 8$$

7. Statistical Analyses

All analyses and summaries will be produced using SAS® version 9.3 (or higher) for windows. Unless otherwise specified, continuous variables will be summarized with descriptive statistics including: the number of observations (n), mean, standard deviation (SD), median, range (minimum and maximum values). For change from baseline, 95% CI will be calculated whenever appropriate. All categorical data will be presented using frequency counts and percentages. Shift tables will be produced for some assessments that contain counts and percentages of subjects in each cross-classification level of baseline versus post-baseline assessment. The by-visit summary of continuous and categorical data will be displayed at protocol planned visits (weeks) and endpoint. Data for unscheduled assessments will be included when determining baseline values, selecting worst result for shift analyses, and for summary of normal/abnormal values. The listings, except for a listing for screen failures, will include all randomized subjects in the database. In general, the subject listings will be sorted by randomized treatment group, subject number and assessment visit and date (and time, if applicable).

7.1 Subject Information

Unless otherwise specified, subject information will be presented by treatment group for the ITT population. The treatment groups will include all Dasotraline (ie, pool two dasotraline groups together) and overall (ie, pooled three treatment groups together). If the safety population differs from the ITT population, similar descriptive statistics will be provided by treatment group, all Dasotraline, and overall for the safety population.

7.1.1 Demographic and Baseline Characteristics

Demographic and baseline characteristics will be summarized by treatment group, and overall for the ITT and PP populations, respectively.

Baseline descriptive statistics (N, mean, SD, median, and range) of demographic characteristics will be provided by treatment group for age at study entry (in years), body weight, height, body mass index (BMI, calculated as weight (kg)/ [height (m)²]), and waist circumference.

The number and percentage of subjects in each of the following categories (and sub-categories) at baseline will also be summarized by treatment group:

- Age group: <40, ≥40 years old;
- Gender: Male, Female;
- Race: white, black or African American, Asian, American Indian or Alaska Native, Native Hawaiian or other Pacific Islander, Other;
- Ethnicity: Hispanic or Latino, Not Hispanic or Latino;
- Baseline BMI category: Underweight/Normal (<25), Overweight (25 to <30), Obesity Class I (30 to <35), Obesity Class II (35 to <40), and Obesity Class III (≥ 40) kg/m²;

321

Baseline descriptive statistics (N, mean, SD, median, and range) of disease characteristics will be provided by treatment group for number of binge eating days per weeks, number of binge eating episodes per weeks, BE-CGI-S, and Y-BOCE-BE total score.

The number and percentage of subjects in each of the following categories (and sub-categories) at baseline will also be summarized by treatment group:

- Baseline number of binge eating days category: 3-4, > 4 to 5, >5 to 6, >6 to 7;
- Baseline severity of BED (number of episodes/week): Mild (3), Moderate (4-7), Severe (8-13), Extreme (≥ 14)

